10.2 Subject Populations for Analysis

There are two principle analysis populations for this clinical study:

10.2.1 Full Analysis Set (FAS) Population – The FAS subject population will consist of all Subjects who i) met all of the pre-operative and intra-operative inclusion criteria and none of the pre-operative and intra-operative exclusion criteria, ii) have been randomized, and iii) received treatment with either Customizable or SOC dressing. Subjects without SSC will need to receive at least 5 days of Customizable or at least 1 day of SOC dressing to be included in this set and completed Visit 9/Day 30 (\pm 4 days). Subjects with SSC prior to Visit 9/ Day 30 (\pm 4 days) will be included in this set regardless of length of Customizable or SOC dressing treatment and treatment follow up. Subject data will be analyzed in the arm to which they were randomized and treated. The primary and secondary effectiveness analyses for this study will be based on the FAS population.

10.2.2 Safety Population (SP) / Intent-to-Treat (ITT) – The safety population / ITT will consist of all Subjects who are randomized and do not withdraw before the attempt to apply the assigned treatment with Customizable or SOC surgical incision dressing regardless of its duration. Subject data will be analyzed in the arm to which they were randomized. All safety results and supportive analyses for this study will be presented based on the safety population.

10.3 Randomization

Subjects who meet all inclusion criteria and no exclusion criteria and who consent to participate in the study will be randomized in a 1:1 ratio to be treated with either Customizable or SOC surgical incision dressing. Due to the variances in complication rates between incision types, a stratified randomization will be used to ensure balance between the groups. The randomization will be stratified for each site and incision type of vertical/transverse and fleur-de-lis. Within each stratum, permuted blocks will be used to achieve equal numbers of Subjects assigned to Customizable or SOC surgical incision dressing. For each stratum, a randomization schedule will be generated to include Subject numbers and treatment assignments with the stratum of transverse/vertical incision starting with 1001 and the stratum of fleur-de-lis incision starting with 2001. Corresponding randomization envelopes will be prepared in sequential order by Subject number to provide randomization to each Investigator.

Randomization envelopes will be prepared corresponding to each row in the randomization schedule. Subject numbers will be printed and labeled clearly on the top of each envelope. Additionally, the envelopes will be color coded for incision type stratum, sealed, and organized by stratum and in ascending by Subject number

Once the Subject has been screened, deemed eligible, and provided informed consent, the next available sequentially numbered randomization envelope within the corresponding stratum according to incision type; a sealed Customizable box and ActiV.A.C. unit will be taken into the operating room with the Subject. Randomization will be conducted in the operating room after closure of the surgical incision and confirmation of intra-operative eligibility. The envelope will be opened prior to surgical incision dressing placement and the assigned treatment arm will be used. If Customizable is not selected, the sealed box and ActiV.A.C. unit will be returned to appropriate storage area.

10.4 General Considerations and Baseline Parameters

Unless otherwise stated, all statistical tests will be performed using 2-sided tests at the 5% significance level. Baseline is defined as the last observation before surgery. Continuous parameters, such as the Subject's age at the time of surgery, will be summarized using descriptive statistics (N, mean, standard deviation, median, minimum and maximum value, and 95% confidence interval) and compared between treatment arms using a 2-sample t-test or a nonparametric test, as appropriate. Categorical parameters, such as gender, will be summarized as a proportion and compared using either a Chi-square test or Fisher's exact test, as appropriate.

10.5 Effectiveness Analyses

10.5.1 Primary Effectiveness Analysis

The primary endpoint for this study is the incidence of SSC up to Visit 9, which will be computed and compared between the two treatment arm (Customizable versus SOC) based on the FAS population. The incidence rate of SSC will be calculated for each treatment arm as follows:

$$\text{SSC rate} = [\text{Number of Subjects who experienced SSC}] / [\text{FAS Population}]$$

Subjects included in the numerator for the incidence computation must have experienced SSC post surgery up to Visit 9. If a Subject has the same SSC event on multiple occasions or experience several events of SSC, the Subject will be counted only once in the numerator for the primary event and the highest intensity.

The incidence of SSC results will be presented by treatment arm and overall. The Fisher's Exact test with a two-sided significance level $\alpha = 0.05$ will be used to compare the SSC

proportions between the two treatment arms. The null and alternative hypotheses are listed below. A 95% confidence interval for the rate difference between the two treatment arms will be provided.

H_0 : *The Customizable and SOC treatment arms have equal incidence rates of SSC*
 $SSC_{CUSTOMIZABLE} = SSC_{SOC}$

H_1 : *The Customizable and SOC treatment arms have different incidence rates of SSC*
 $SSC_{CUSTOMIZABLE} \neq SSC_{SOC}$

If the incidence rate of SSC of Customizable is smaller than the incidence rate of SSC of SOC dressing (i.e. $SSC_{CUSTOMIZABLE} < SSC_{SOC}$) and the P-value from the above Fisher's Exact test is below 0.05 (i.e. P-value < 0.05), then we conclude that the incidence rate of SSCs decreased statistically significantly in Customizable compared with SOC dressing in this clinical study. As supportive analysis, the incidence of SSC will be compared using the ITT population.

As additional supportive analysis, logistic regression analysis may be performed with the ITT and FAS populations. Covariates to be included in the logistic regression will be incision type (i.e., transverse, fleur- de-lis, and vertical incisions), total incision length, BMI, and any other baseline covariates identified following the methods proposed by Hosmer and Lemeshow. Once covariates have been determined, logistic regression will be used to evaluate the treatment with adjustment for the statistically significant covariates. Hospital and hospital by treatment effects will be included as random effects in the logistic regression model to evaluate heterogeneity of treatment effect. If more than three covariates are identified, the treatment will also be evaluated by separate models controlling for each covariate with random effects of hospital and hospital by treatment.

10.5.2 Secondary Effectiveness Analyses

10.5.2.1 Number of Clinically Relevant Interventions (CRI)

The secondary endpoint for this study is the number of CRI of the surgical incision. The number of CRI will be computed and compared between the two treatment arms (Customizable versus SOC) based on the FAS population. The number of CRIs will be calculated for each treatment arm as follows:

The Number of CRI = Number of CRI experienced per Subject in FAS Population

If a Subject has the same CRI for a complication on multiple occasions, or experiences multiple CRIs post surgery up to Visit 9, each CRI will be counted separately until the complication resolves or the study ends. The number of CRI results will be presented by treatment arm and overall. Depending on the estimate of the dispersion of the data, a zero-inflated Poisson (ZIP) or zero-inflated negative Binomial (ZINB) model will be used to model the number of CRI to account for excess zeros. Treatment factor, number of days in study from time of therapy initiation, and significant covariates (e.g. BMI, incision type), will be included as independent variables in the analysis of the number of CRIs.

The hypothesis for testing the treatment effect is as follows:

$$H_0: \text{The parameter estimate for the treatment effect equal to 0}$$
$$\beta_{\text{treatment}} = 0$$

$$H_1: \text{The parameter estimate for the treatment effect not equal to 0}$$
$$\beta_{\text{treatment}} \neq 0$$

If the number of CRI for one treatment group is inadequate for the proposed analysis, the incidence of CRI will be calculated for each treatment arm as follows:

$$\text{CRI rate} = [\text{Number of Subjects who experienced CRI}] / [\text{FAS Population}]$$

If a Subject has the same CRI event on multiple occasions or experience several events of CRI, the Subject will be counted only once in the numerator.

The incidence of CRI results will be presented by treatment arm and overall. The Fisher's Exact test with a two-sided significance level $\alpha = 0.05$ will be used to compare the CRI proportions between the two treatment arms. The null and alternative hypotheses are listed below. A 95% confidence interval for the rate difference between the two treatment arms will be provided.

$$H_0: \text{The Customizable and SOC treatment arms have equal incidence rates of CRI}$$
$$\text{CRI}_{\text{CUSTOMIZABLE}} = \text{CRI}_{\text{SOC}}$$

$$H_1: \text{The Customizable and SOC treatment arms have different incidence rates of CRI}$$
$$\text{CRI}_{\text{CUSTOMIZABLE}} \neq \text{CRI}_{\text{SOC}}$$

As supportive analysis, the incidence of CRI will be compared using the ITT and FAS populations.

Covariates to be included in the logistic regression will be incision type (i.e., transverse, fleur-de-lis, and vertical incisions), total incision length, BMI, and any other baseline covariates following the methods proposed by Hosmer and Lemeshow. Once covariates have been

determined, logistic regression will be used to evaluate the treatment with adjustment for the statistically significant covariates. Hospital and hospital by treatment effects will be included as random effects in the logistic regression model to evaluate heterogeneity of treatment effect. If more than three covariates are identified, the treatment will also be evaluated by separate models controlling for each covariate with random effects of hospital and hospital by treatment.

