3.3 Secondary Study Endpoint

3.3.1 Clinically Relevant Interventions

Incidence of clinically relevant interventions (CRI) of the surgical incision in Subjects managed with Customizable as compared to the control group managed with a SOC surgical incision dressing. For this study, clinically relevant interventions are defined as the following:

- Antimicrobial treatment of SSI
- Percutaneous and open drainage of the surgical incision (by surgeon)
- Debridement of the surgical incision
- Re-operation related to the surgical incision
- NPWT applied to the open surgical incision

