5.7.2 Clinically Relevant Interventions (CRI)

If a SSC requires intervention, the procedure must be documented. Any subsequent CRI for a SSC that resolves and then recurs will be documented as a separate CRI.

5.7.2.1 Antimicrobial treatment of SSI: administration of antibiotics, antifungals, or other antimicrobials for the treatment of an infection related to the surgical incision.

5.7.2.2 Percutaneous or Open Drainage (by surgeon): decompression of the fluid accumulation using either:

1) Percutaneous drainage of incisional fluid;

- OR -

2) Open technique (at bedside) drainage of incisional fluid;

- OR -

3) Open surgical intervention (in a procedure room or operating room) drainage of incisional fluid.

If infection is suspected, Customizable should be discontinued, cultures should be obtained, and clinically significant results documented as an adverse event.

5.7.2.3 Debridement: Removal of necrotic, damaged, or infected wound tissue either at the bedside or in the operating room. Debridement involving muscular fascia or deeper tissues should be documented as reoperations.

5.7.2.4 Reoperation: Procedure requiring dissection deeper than the skin and subcutaneous tissue, repair of the muscular fascia, entry into the retro-peritoneum, renal transplant revision or graft removal, flaps, and skin graft procedures.

5.7.2.5 NPWT: Application of NPWT for management of the opened surgical incision (wound).

[figure not shown]

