4.2 Secondary Endpoint

The secondary endpoint for this study is the subject incidence of clinically relevant interventions (CRI) of the surgical incision in Subjects managed with Customizable™ as compared to the control group managed with a SOC surgical incision dressing. For this study, clinically relevant interventions are defined as the following:

- Antimicrobial treatment of SSI
- Percutaneous and open drainage of the surgical incision (by surgeon)
- Debridement of the surgical incision
- Re-operation related to the surgical incision
- NPWT applied to the open surgical incision

No analysis for the secondary endpoint will be performed due to the early termination of the study.

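### The stated secondary endpoint is CRI incidence, but Protocol 10.5.2.1 first tests one unassigned coefficient of a zero-inflated count model, which is a weaker test of whether subjects need an intervention

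*Protocol*

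**What the plan says.** The documents describe the secondary endpoint in two ways.

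- Protocol 3.3.1: "Incidence of clinically relevant interventions (CRI) of the surgical incision in Subjects managed with Customizable", compared with the control group.
- SAP 4.2: "The secondary endpoint for this study is the subject incidence of clinically relevant interventions (CRI) of the surgical incision".
- Protocol 10.5.2.1: "The secondary endpoint for this study is the number of CRI of the surgical incision".

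For the count, Protocol 10.5.2.1 states that, depending on the estimated dispersion, "a zero-inflated Poisson (ZIP) or zero-inflated negative Binomial (ZINB) model will be used to model the number of CRI". Treatment, days in study and significant covariates are the independent variables. The null hypothesis is "The parameter estimate for the treatment effect equal to 0", written as a single beta for treatment. The section does not say which part of the model that beta belongs to, or whether it is tested by Wald or likelihood ratio.

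Fisher's exact test on CRI incidence, with a 95% confidence interval for the rate difference, applies if the number of CRIs in one group is inadequate for the model. No threshold is given. The end of the section adds a supportive comparison of incidence in the ITT and FAS populations.

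SAP 4.2 then drops the secondary analysis because the study ended early.

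**The concern.** A zero-inflated model has two treatment effects: one on the probability of being an excess zero, and one on the mean count in the latent class that can have events. Neither is the effect on incidence. An incision dressing would be expected to act mainly on whether a subject needs any intervention. If the single beta is the count coefficient and treatment is also in the zero part, that effect is absorbed by a coefficient that nobody tests.

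The first-line test could then miss a large fall in the endpoint that 3.3.1 defines. Because neither the coefficient nor the condition for switching to Fisher is fixed, the choice of secondary test could also be made after the data are seen.

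**Working it through.** **Inputs.** Two-sided alpha 0.05 (Protocol 10.4). Rates of 35% and 8.75% and 44 per arm (Protocol 10.1). These rates are for SSC. The documents give no CRI rates or counts per subject, so the SSC rates are borrowed as an assumption and the number of CRIs per affected subject is varied.

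**Step 1: the plan's own figure.** Exact Fisher power is the sum of Bin(x; 44, 0.35) × Bin(y; 44, 0.0875) over all tables (x, y) with Fisher p ≤ 0.05. The result is 80.67%, which agrees with the approximately 80% in Protocol 10.1.

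**Step 2: what the model tests.** In a zero-inflated Poisson (ZIP) model, with excess-zero probability π and count mean λ,

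P(Y = 0) = π + (1 − π)e^(−λ), so incidence = (1 − π)(1 − e^(−λ)).

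Suppose affected subjects have the same distribution of CRIs in both arms, so λ is common. Take λ = 0.8, where 1 − e^(−0.8) = 0.551 and the mean number of CRIs per affected subject is 0.8/0.551 = 1.45. Then

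- SOC: 1 − π = 0.35/0.551 = 0.64
- Customizable: 1 − π = 0.0875/0.551 = 0.16

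The whole 75% reduction lies in π. The count coefficient is exactly zero, so with treatment in both parts a valid test of it rejects at about the alpha level at any sample size.

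**Step 3: simulation at 44 per arm.** Incidence 35% v 8.75%, zero-truncated Poisson counts with the same λ in both arms, likelihood-ratio tests. Percentage of runs rejecting:

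| Mean CRIs per affected subject (λ) | Fisher on incidence | Count coefficient, treatment in both parts | Count coefficient, treatment in count part only | Zero-part coefficient |
|---|---|---|---|---|
| 1.45 (0.8) | 79–80 | 4 | 71–77 | 25 |
| 1.93 (1.5) | 83 | 6 | 47 | 52 |
| 2.72 (2.5) | 79 | 8 | 40 | 74 |
| 4.07 (4.0) | 77 | 7 | 20 | not run |

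The middle three columns come from 150 runs per setting, with a further 600 at λ = 0.8; Monte Carlo error is about 2–4 points. The last column comes from separate sets of 300 runs, in which Fisher had 81%, 83% and 79%. A further rerun gave the same pattern: Fisher about 79%, then 5–7%, 35–72% and 35–68% for the three readings.

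**Step 4: is this only a small-sample effect?** At 200 per arm (60 runs each, λ = 1.5 and 2.5) Fisher reached 100% in both settings. The two-part count coefficient had 8% and 12%, and the count-only version 93% and 52%. The two-part result does not recover with sample size, as Step 2 predicts.

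**Step 5: a joint test.** A 2-degree-of-freedom test of treatment in both parts gave 79–85%, against 81–88% for Fisher. The model can therefore carry the information, but the single-beta hypothesis as written is not this test.

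**The case against.** **No consequence for the final analysis.** SAP 4.2 cancels the CRI analysis and SAP 9 plans no other. This stands: under the abbreviated SAP no zero-inflated model is fitted. What remains is a flaw in the protocol's method, which is the only one written for a CRI comparison.

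**Incidence is not abandoned.** Fisher is the fallback, and the end of 10.5.2.1 compares incidence as supportive. At 8.75% of 44 about 4 Customizable subjects would have a CRI (0.0875 × 44 = 3.9), so the fallback could well apply. At the interim review (SAP 10) SSC occurred in about 5 of 29 (17.2%) and 1 of 32 (3.1%) subjects, and 5.7.2 ties CRIs to SSCs. A reader might infer that the incidence question goes unanswered; the documents do not support that. The defect is the ranking of the two analyses and the missing threshold.

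**Error rate.** A reader might also infer that the test exceeds 5%. Wald tests of the two-part count coefficient did reject in 8–20% of runs with no effect (51 per arm, 20–25% in both arms). Likelihood-ratio tests rejected in about 2–8% across the reruns. The protocol does not specify Wald, so inflation is not shown for the plan as written.

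**The scenarios disfavour a count test.** Equal CRIs per affected subject is an assumption. If the dressing also reduced repeat interventions, a count analysis would gain. This stands as a limit on the size of the loss.

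**Counting rules.** Protocol 10.5.2.1 says "each CRI will be counted separately until the complication resolves or the study ends"; 5.7.2 says "Any subsequent CRI for a SSC that resolves and then recurs will be documented as a separate CRI". It is tempting to call these contradictory, but one covers the time before resolution and the other recurrence after it, so they can be read together. A single statement would still help.

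**Days in study as a covariate.** It is measured after randomisation. But the FAS leaves out SSC-free subjects without Visit 9, so shortened follow-up remains only among subjects with an SSC. This adds little.

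**Conclusion.** The point holds for the protocol's plan. The endpoint is incidence in Protocol 3.3.1 and SAP 4.2 and a count in Protocol 10.5.2.1, and the first-line hypothesis is one coefficient with no stated place in a two-part model.

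If treatment mainly changes whether a subject needs a CRI, every single-coefficient reading was below Fisher in the settings run: about 4–8%, 20–77% or 25–74%, against about 80%. The loss is near total for the two-part count coefficient. It is small at the favourable end of the other two readings, where the closest gaps are about 3 to 5 points (76.8% v 80.3% for count part only; 74% v 79% for the zero part).

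These figures rest on borrowed SSC rates, equal CRIs per affected subject and a ZIP without covariates. The negative binomial version was not simulated. No claim is made about type I error, and the abbreviated final analysis is not affected.

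**What to change.** In Protocol 10.5.2.1, name subject-level CRI incidence as the secondary endpoint, in line with 3.3.1 and SAP 4.2. Make the Fisher test and the 95% confidence interval for the rate difference, both already written there, the secondary analysis. The undefined switch for inadequate counts then falls away.

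Move the number of CRIs per subject to a supportive or descriptive summary under one counting rule, stated the same way in 5.7.2 and 10.5.2.1. If a zero-inflated model is kept as supportive, test treatment jointly in both parts and name the test.

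This should not reinstate a confirmatory CRI test now. SSC results by arm were seen at the interim review (SAP 10), so any CRI comparison in the study report should give incidence by arm with a confidence interval and be labelled descriptive or post hoc.

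The cost is wording and simpler programming. The one loss is a formal secondary test on repeat interventions.

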10.5.3 Supportive / Supplementary Effectiveness Analysis

Supportive, supplementary, and descriptive analyses will also be performed using specified and subset populations on data collected including other data specified in Section 3.1, which includes incision type, location, length, material used for hernia repair, length of therapy, interventions, pain assessments using the visual analog scale, etc.

The specifics of any additional analyses will be determined at the time of analysis. In general, summary statistics will include N, mean, standard deviation, median, range (minimum, maximum) and 95% confidence interval for continuous variables, and frequencies and percentages for categorical variables. If appropriate, continuous variables will be compared using a 2-sample t-test or Wilcoxon Rank-Sum test and categorical variables will be compared using Fisher's Exact test or Chi-Square test. When possible, OLS, logistic regression, and time-to-event analysis, will be performed to control for covariates, such as BMI, incision length, etc., to confirm effect of Customizable versus SOC.

Given the exploratory nature of the supportive or supplementary analyses, no adjustment for multiplicity will be made in these analyses.

10.6 Safety Analyses

Safety analyses will be carried out using the Safety Population to allow a benefit/risk assessment within the same study population.

All AEs recorded during the course of the study will be coded according to the MedDRA (version 13.0) classification system. An event will be considered as *treatment emergent* if the time of onset is after placement of study treatment.

Number and percentage of treated subjects who experienced at least one adverse event in each system organ class by preferred term will be used to summarize all serious and non-serious adverse events. Summary tables by treatment arm and overall will be provided of incidences for all treatment emergent adverse events, treatment – related adverse events, adverse events by maximum severity, serious adverse events, and adverse events that led to study discontinuation. In any given category (e.g., system organ class or preferred term) a Subject

will be counted only once. If a Subject has the same adverse event on multiple occasions, only the one with maximum severity will be presented. The denominator for the calculation of percentages will be the number of Subjects in the sub-arm of Subjects being tabulated and not the number of events.

